6.3. Treatment Assignment

Subjects will be assigned to study treatment in accordance with the randomisation schedule. The randomisation code will be generated by GSK using a validated computerized system. Subjects will be randomized using an IRT System, RAMOS NG. The study will use country based randomisation to allocate treatments. Once a randomisation number is assigned to a subject it cannot be reassigned to any other subject in the study.

Subjects who meet the eligibility criteria and successfully complete the 2-week run-in period will be randomized (1:1) to one of the following study treatment regimens:

- FF/UMEC/VI 100mcg/62.5mcg/25mcg and placebo, both via the ELLIPTA once daily in the morning
- or,
- FF/VI 100mcg/25mcg and UMEC 62.5mcg, both via the ELLIPTA once daily in the morning.

The randomization will be stratified based on **long-acting bronchodilator** usage during the run-in (none, one or two **long-acting bronchodilators** per day).

Subjects will be instructed to take one dose each morning from each ELLIPTA.

The duration of treatment for each subject is 24 weeks. On the morning of each clinic study visit, subjects will refrain from taking their morning dose of study treatment until instructed to do so by clinic personnel. Study treatment will be given at the clinic at approximately the same time of day as Randomisation (V2). On the other days during the treatment period (*i.e.* “non-clinic days”), subjects will be instructed to take their study treatment each morning at approximately the same time of day. The IRT system will provide a means for site-based allocation of drug. Each investigator will be supplied with sufficient supplies to conduct the trial. Additional treatment packs will be supplied as needed to the sites. Details of how to use the IRT system to randomize subjects is provided in the SPM.

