Study Design	
 This is a phase IIIB, 24-week, randomised, double-blind, parallel group, multicenter study evaluating FF/UMEC/VI (100/62.5/25mcg) delivered via a single ELLIPTA ('closed' triple) plus matching placebo ELLIPTA versus FF/VI (100/25mcg) + UMEC (62.5mcg) delivered via two ELLIPTAs ('open' triple), all taken once daily. Subjects will be randomized 1:1 to either FF/UMEC/VI or FF/VI+UMEC. The randomisation will be stratified based on long-acting bronchodilator usage during the run-in (none, one or two long-acting bronchodilators per day). A study with 816 evaluable subjects for the primary analysis will have 90% power to determine non-inferiority of FF/UMEC/VI to FF/VI+UMEC based on trough FEV1 at Week 24, an estimate of residual standard deviation (SD) for trough FEV1 at Week 24 of 220mL, at the one-sided 2.5% significance level when the margin of non-inferiority is 50mL and the true mean treatment difference is assumed to be 0mL. Based on approximately 20% of subjects who are randomized discontinuing study treatment or being excluded from the mPP population at Week 24, approximately 1020 subjects will be randomised
Planned Analyses	
 No interim analyses are planned for this study.

Overview	Key Elements of the RAP
	
 All decisions regarding final analysis, as defined in this RAP document, will be made by Source Data Lock (SDL) prior to Study Data Tabulation Model (SDTM) Database Freeze (DBF) of the study data except for the identification of protocol deviation (PD) that require treatment details. The PD of taking incorrect treatment and treatment non-compliance (based on active treatment) will be identified following DBF.

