7.1.2. Planned Efficacy Statistical Analyses

Primary Statistical Analyses
Endpoint(s)

 ○ Trough FEV1
Model Specification

 ○ The primary endpoint of change from baseline in trough FEV1 will be analyzed in the mPP population, using a mixed model repeated measures (MMRM) analysis, including trough FEV1 recorded at each of Week 4, 12 and 24. The model will include covariates of baseline FEV1, stratum (number of long-acting bronchodilators per day during the run-in), Visit, geographical region, treatment and Visit by baseline interaction. A Visit by treatment interaction term will also be included to allow treatment effects to be estimated at each visit separately. ○ The variance-covariance matrix will be assumed unstructured. ○ Two models will be fitted; one with a response variable of trough FEV1, and one with a response variable of change from baseline in trough FEV1.
Handling of Missing Data for Analysis

 ○ No data were collected for subjects who prematurely discontinued study treatment. All missing and excluded data will be assumed to be Missing at Random (MAR). Sensitivity analyses to investigate the impact of this assumption will be conducted as described below.
Model Checking & Diagnostics

 ○ Refer to Appendix 11: Model Checking and Diagnostics for Statistical Analyses.
Model Results Presentation

 ○ Least Square (LS) mean and LS mean change from baseline with their corresponding standard errors (SEs) will be presented for each treatment by Visit, together with estimated treatment differences (FF/UMEC/VI vs. FF/VI+UMEC) and the corresponding 95% confidence intervals (CIs). ○ A plot of LS means change from baseline and 95% CIs from the model will be generated for each treatment by Visit.
Example SAS Code

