<pre>proc mixed data=<dataset>; class treatment visit cengroup stratum subjid; model endpoint=baseline stratum visit cengroup treatment visit*baseline visit*treatment / ddfm=kr; repeated visit/ subject=subjid type=un; lsmeans visit*treatment / cl diff e om=OMdset at (baseline)=(&blm.); ods output lsmeans=lsmeans; ods output diffs=diffs; run;</pre> 
where OMdset is a dataset with a row for every subject-visit combination that contains all of the covariates and blm is a macro variable containing the mean baseline for the subjects used in the analysis. This is used to derive the LS means using coefficients which are based on the subjects used in the analysis.

Sensitivity and Supportive Statistical Analyses

 ○ The above will be repeated for the ITT population. LS mean and LS mean change from

Sensitivity and Supportive Statistical Analyses

baseline with their corresponding SEs will be presented for each treatment by Visit, together with estimated treatment differences and the corresponding 95% CIs.

- A “tipping point” sensitivity analysis of trough FEV1 at Week 24 will be conducted for the mPP Population. This will explore the impact of missing data by using differing assumptions regarding the mean treatment effect in subjects who discontinue study treatment or have data excluded from the mPP Population analyses. Mean treatment effects investigated will range from a change from baseline of -150mL to +150mL in increments of 50mL. For each value of the assumed mean change from baseline on FF/UMEC/VI, the full range of values for the assumed mean change from baseline for FF/VI+UMEC will be investigated; thus including scenarios where subjects who discontinue FF/UMEC/VI have a lower treatment effect than those who discontinue FF/VI+UMEC and vice versa. The analysis results will be used to explore the conditions under which the conclusion of non-inferiority no longer holds.

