8.1.2.2. TDI

Secondary Statistical Analyses
Endpoints
● TDI focal score
Model Specification, Checking, Results Presentation and SAS code
● Same as for trough FEV1, see Section 7.1.2
● BDI will be used in place of baseline.
● Visit includes week 12 and 24.

8.1.2.3. Proportion of Responders according to SGRQ Total Score and Responders according to TDI

Endpoints
● Proportion of Responders according to SGRQ total score
● Proportion of Responders according to TDI
Model Specification
● Generalized Linear Mixed Model
● Terms in the model: Dependent Variable: Response (Yes/No) Categorical : treatment group, stratum, geographical region, visit Continuous : Baseline (for SGRQ total score) or BDI Interaction : baseline*Visit, treatment*Visit Repeated : Visit
● The model will be fit with an unstructured variance-covariance matrix
● One single model to include all visits
○ SGRQ: include Week 12 and 24
○ TDI: include Week 12 and 24
Handling of Missing Data for Analysis
● Subjects with missing on-treatment data and a subsequent non-missing on-treatment scheduled assessment will not be considered as a responder/non-responder but will be left as missing.
● Subjects that have withdrawn from the study prior to the visit in question will be imputed as

non-responders at all visits post-withdrawal where the assessment was expected to be performed.

 Refer to Appendix 11: Model Checking and Diagnostics for Statistical Analyses.
Model Results Presentation

 Number and percentage of responders and non-responders for each treatment at each Week Odds ratio for comparison between FF/UMEC/VI and FF/VI+UMEC with associated 95% CI
Example SAS Code
<pre>proc glimmix data=filename ; class treatment stratum visitnum subjid centgroup; model respond(event="1") = treatment base stratum visitnum centgrp visitnum*base visitnum*treatment / dist=binary link=logit ddfm=kr solution; lsmeans visitnum*treatment / cl diff or om ; random visitnum / subject=subjid residual type=un; ods output diffs=differs; run;</pre>

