8.1.2.4. COPD Exacerbations

Secondary Statistical Analyses
Endpoints

 Time to first on-treatment moderate/severe COPD exacerbation
Model Specification

 Cox's proportional hazards model 
Terms in the model:
 
Dependent variable: time to first on-treatment moderate/severe exacerbation
 
Categorical: treatment group, gender, exacerbation history (0, 1, >=2 moderate/severe exacerbations in the last 12 month at screening), smoking status (screening), stratum and geographical region.
 
Continuous: % predicted FEV1 at Baseline
 
 Use the 'exact' method for handling ties. (If the analysis will not run using the 'exact' method, then the 'Efron' method for handling ties will be used instead.)
Handling of Missing Data for Analysis

 Subjects who withdrew from the study prior to experiencing a COPD exacerbation will be considered censored at random.
Model Checking & Diagnostics

 Refer to Appendix 11: Model Checking and Diagnostics for Statistical Analyses.
Model Results Presentation

 Hazard ratio for comparison between FF/UMEC/VI and FF/VI+UMEC with associated 95% CI
Example SAS Code

Secondary Statistical Analyses
proc phreg data=<dataset> ; model timeto1*eventflag(0)=treatment fevpred stratum cengroup smokehis hxf_exac / risklimits ties=exact; run;

Secondary Statistical Analyses
Endpoints

 • Time to first on-treatment moderate/severe COPD exacerbation
Model Specification

 ○ A Kaplan-Meier analysis will also be performed for figure showing Kaplan-Meier survivor functions of the proportion of subjects with a first exacerbation over time for each treatment group separately plotted on the same figure.
Example SAS code
proc lifetest data=destin outsurv=survest; time timeto1*eventflag(0); strata treatment; run;
Model Results Presentation

 ○ Probability of having an event, 95% CI and first quartile time to exacerbation (estimate of the time at which 25% of subjects in each treatment group would have had an exacerbation) ○ Figure showing Kaplan-Meier survivor functions of the proportion of subjects with a first exacerbation over time for each treatment group separately plotted on the same figure.

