
Randomization stratum, long-acting bronchodilator usage during the run-in, will be derived based on the RMC classification and will be grouped into the following 3 categories:
 
 • None • One long-acting bronchodilator per day • Two long-acting bronchodilators per day 
Long-acting bronchodilator is defined as any COPD medication in Respiratory Medication Class (MRC) under 'Long-acting beta-2 agonist – Group 2' or 'Long-acting beta-2 agonist – Group 3' or 'Long-acting anticholinergic'.
 
Based on RAMOS NG record, the number of subjects used none long-acting bronchodilator during run-in is very small (ie. <1% of randomized subjects). Therefore, the combined stratum with 2 categories will be used in the statistical analysis, ie, none and one long-acting bronchodilator per day will be combined into one category in analysis.
 
Ranodmisation stratum is also collected at randomization in RAMOS NG. Both randomization stratum (derived and collected) will be listed.

Medical Conditions and Concomitant Medications
Cardiovascular Risk Factors

Subjects with at least one of the following current or past medical conditions at Screening will be classed as having a cardiovascular (CV) risk factor at screening. The number of CV risk factors at Screening (0, 1, or ≥2) will be derived.
 
 • Angina pectoris • Coronary artery disease • Myocardial infarction • Arrhythmia • Congestive heart failure • Hypertension • Cerebrovascular accident • Carotid or aorto-femoral vascular disease, • Diabetes mellitus • Hypercholesterolemia
COPD Concomitant medications

COPD concomitant medications will be grouped into the following RMCs based on pre-defined code lists derived from ATC classifications:
 
 • Antiinfectives (antibiotics, antifungals, antivirals, antiseptics) • Short-acting anticholinergic

Medical Conditions and Concomitant Medications

• Short-acting beta-2 agonist• Long-acting anticholinergic• Long-acting beta-2 agonist• Xanthine• PDE4 Inhibitor• Corticosteroid - inhaled• Corticosteroid - depot• Corticosteroid - systemic oral parenteral and intra-articular• Corticosteroid - other• Leukotriene receptor antagonist• Nedocromil or cromolyn sodium• Mucolytic• Oxygen• Other medication given for exacerbation• Other COPD medication
COPD medication combination

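### The example PHREG code for time to first exacerbation omits gender and has no CLASS statement, so it does not fit the Cox model specified above it (minor)

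*SAP*

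**What the plan says.** The endpoint is one of the listed secondary endpoints (SAP 2.2). For it, SAP 8.1.2.4 gives the Cox terms as "Categorical: treatment group, gender, exacerbation history (0, 1, >=2 moderate/severe exacerbations in the last 12 month at screening), smoking status (screening), stratum and geographical region", and adds percent predicted FEV1 at baseline as the only continuous term.

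The example code in the same table goes straight from the PROC PHREG line to "model timeto1*eventflag(0)=treatment fevpred stratum cengroup smokehis hxf_exac / risklimits ties=exact; run". The variables are treatment, percent predicted FEV1, stratum, region (`cengroup`), smoking and exacerbation history.

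Two other model examples in the SAP bear on how region is meant to be handled:
- The MIXED example in 7.1.2 declares "class treatment visit cengroup stratum subjid" and uses the same `cengroup` in its MODEL statement.
- The GLIMMIX example in 8.1.2.3 declares "class treatment stratum visitnum subjid centgroup", but its MODEL statement uses `centgrp`, a different name.

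**The concern.** The example contradicts the specification it is meant to illustrate, in two ways: gender is missing, and nothing is declared categorical.

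A programmer who copies the code meets one of two outcomes. If any term is stored as character, PHREG stops, which is a nuisance but detects itself. If every term is numeric, the code runs and returns an ordinary-looking hazard ratio from a different model. The second case matters more, because nothing in the output shows that the fitted model is not the planned one.

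A further conditional issue is the direction of the ratio. Without CLASS, PHREG reports the hazard ratio per unit increase in the treatment variable, so the arm in the numerator depends on how that variable is coded.

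**Working it through.** The plan gives no figure to reproduce here. The check compares specification and code term by term, counting (levels − 1) for each categorical term and 1 for the continuous term, against 1 for each variable entered without CLASS.

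| Term | Levels and source | df specified | df as printed |
|---|---|---|---|
| Treatment | 2 (SAP 10.5.1) | 1 | 1 |
| Gender | 2 (Protocol 5.1) | 1 | 0 |
| Exacerbation history | 3 (SAP 8.1.2.4) | 2 | 1 |
| Smoking status | 2, assumed current/former (Protocol 5.1; SAP 10.6.2) | 1 | 1 |
| Stratum | 2 (SAP 10.6.2) | 1 | 1 |
| Region | 4 (SAP 10.8.1) | 3 | 1 |
| Percent predicted FEV1 | continuous | 1 | 1 |
| **Total** | | **10** | **6** |

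The gap of 10 − 6 = 4 is 1 for gender, 2 for region and 1 for exacerbation history.

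- **Either correction alone.** CLASS without gender gives 10 − 1 = 9. Gender without CLASS gives 6 + 1 = 7. Both are needed.
- **Two-level terms.** Numeric entry does not change the fit for these. Stratum is one of them, because SAP 10.6.2 says "none and one long-acting bronchodilator per day will be combined into one category in analysis".
- **Exacerbation history.** Inclusion criterion 10 requires at least one prior moderate or severe event, so level 0 should be nearly empty. If it is empty, the specified model has 10 − 1 = 9 df and the gap is 3. It need not be empty: the ITT population keeps subjects with eligibility deviations (SAP sections 4 and 10.1.1), and SAP Table 1.10 tabulates such deviations for ITT. SAP 10.6.2 also groups history as 0, 1, 2 and 3 or more, and the coding of `hxf_exac` is not given.
- **Pre-built indicators.** Four regions would need three indicator variables. The code has one, `cengroup`, so indicators built beforehand do not explain the missing CLASS statement, and they would not explain the missing gender term.

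**Illustration of the effect on the treatment log hazard ratio.** All effects and event rates here are assumed. In 400 simulated data sets per scenario, 1059 subjects were drawn at the SAP 10.8.1 region sizes (398 + 252 + 215 + 194 = 1059), with a true hazard ratio of 1.0 or 0.85. The printed handling (region 1 to 4 as a slope, no gender) was compared with the specified handling (region 3 df, gender included). Exacerbation history was not varied. Assumed log hazard ratios were region 0/0.4/−0.3/0.3 and gender 0.2 (moderate), or region 0/0.7/−0.5/0.6 and gender 0.4 (strong).

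| Arm allocation | 95th percentile shift, moderate | 95th percentile shift, strong |
|---|---|---|
| Balanced within region and stratum | 0.020 to 0.025 | 0.038 to 0.044 |
| Simple randomisation | 0.037 to 0.039 | 0.073 to 0.076 |

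The standard error was 0.083 to 0.117 in the balanced runs. On the ratio scale, 0.85 × exp(±0.025) = 0.83 to 0.87, 0.85 × exp(±0.044) = 0.81 to 0.89, and 0.85 × exp(±0.076) = 0.79 to 0.92. For comparison, a 95% interval with an assumed standard error of 0.10 is exp(ln 0.85 ± 1.96 × 0.10) = 0.70 to 1.03.

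Protocol 6.3 says "The study will use country based randomisation to allocate treatments", and randomisation is stratified, so the balanced row is the closer one. Balance is not exact, because SAP 10.4.1 replaces the randomised stratum with the calculated one where they differ.

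**Direction.** SAP 10.5.1 lists randomisation code 1 for FF/UMEC/VI and 2 for FF/VI+UMEC. If `treatment` carried those codes, the printed ratio would be FF/VI+UMEC over FF/UMEC/VI. A ratio of 0.85 (0.70 to 1.03) would appear as 1/0.85 = 1.18 (0.97 to 1.43).

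**The case against.** The strongest reply is that the block is headed as an example and the text above it is explicit. The endpoint is secondary, comparisons are not adjusted for multiplicity, and no treatment p-values are displayed (SAP 10.10.1). A character variable would stop the program at once. The SAP's code blocks also look like sketches: the GLIMMIX example declares one region name and models another.

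Most of this stands, and it is why the point is minor. It does not remove the fault, because example code exists to be copied and the all-numeric case gives no warning. The GLIMMIX slip cuts both ways. It means only the MIXED example is a clean comparator, and it is another reason to proofread the code.

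A reader might infer that the sponsor deliberately dropped gender. Nothing in the SAP says so: 8.1.2.4 still lists it, and the only change declared in SAP 2.1 is the renaming of a population.

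A reader might also infer that the reported hazard ratio will be inverted. The documents do not support that. The codes in 10.5.1 belong to the randomisation system, and the SAP does not say that the analysis variable uses them. The intended order can be inferred from 7.1.2, which presents "estimated treatment differences (FF/UMEC/VI vs. FF/VI+UMEC", and from Appendix 11, which makes FF/VI+UMEC the reference for the responder model. The Cox block of Appendix 11 names no reference arm.

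**Conclusion.** The point holds as a minor inconsistency. The example code as printed does not fit the specified Cox model: 6 df against 10, or 9 if exacerbation-history level 0 is empty. Gender is absent, region becomes a linear trend, and so does exacerbation history if it has more than two levels. The count assumes that smoking status has two levels. Character storage of any term, not only region, would stop the code.

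The planned analysis is sound as written and does not change. It would be tempting to attach a firm size to the distortion of the hazard ratio. The documents do not support one, since event rates, covariate effects and the achieved balance between arms are all unknown. The illustration shows only that the shift is probably small beside the sampling error.

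**What to change.** Correct the PHREG example in SAP 8.1.2.4:
- add a CLASS statement for treatment (reference FF/VI+UMEC), gender, exacerbation history, smoking status, stratum and region;
- add gender to the MODEL statement.

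In the same edit, use one name for the region variable in the GLIMMIX example of 8.1.2.3, where `centgroup` and `centgrp` now differ.

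Optionally, state in 8.1.2.4 and in the Cox block of Appendix 11 that the hazard ratio is FF/UMEC/VI relative to FF/VI+UMEC.

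The cost is one added line, one added term, one corrected name and at most a sentence in each of two places. It is sensible to do this before source data lock, although bringing an example into line with unchanged text is not itself an analysis decision of the kind SAP section 1 ties to that date.

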8.2. Safety Analyses

8.2.1. Overview of Planned Analyses

The safety analyses generally will be based on the ITT population.

Table 5 provides an overview of the planned analyses, with the detailed list of data displays being presented in Section 10.13.

Table 5 Overview of Planned Safety Analyses

	Absolute				Change from Baseline			
	Summary		Individual		Summary		Individual	
	T	F	F	L	T	F	F	L
Exposure								
Exposure Data	Y		Y	Y				
Adverse Events (AEs)								
Overview of On-Treatment AEs	Y							
On-Treatment AEs	Y ¹⁰							
Post-Treatment AEs	Y							
On-Treatment Drug-Related AEs	Y							
Pre-Treatment SAEs	Y ^{1,2}							

	Absolute				Change from Baseline			
	Summary		Individual		Summary		Individual	
	T	F	F	L	T	F	F	L
On-Treatment SAEs	Y							
Post-Treatment SAEs	Y							
On-Treatment Fatal SAEs	Y							
On-Treatment Drug-Related SAEs	Y							
Pre-Treatment SAEs Leading to Withdrawal from Study	Y ¹							
On-Treatment AEs Leading to Withdrawal from Study	Y							
On-Treatment AEs of Special Interest	Y							
On-Treatment SAEs of Special Interest	Y							
Relationship of AE System Organ Class, Preferred Term and Verbatim Text	Y ¹							
On-treatment Common Non-Serious AEs (3% or More of Subjects in Any Treatment Group)	Y							
10 Most Frequent On-treatment Adverse Event in Each Treatment Group	Y							
On-treatment Adverse Events by System Organ Class and Maximum Intensity	Y							
Subject Numbers for Individual AEs				Y ¹				
All AEs				Y ¹				
Non-Fatal Serious AEs				Y ¹				
Fatal AEs				Y ¹				
AEs Leading to Withdrawal from Study				Y				
Subject Numbers for On-Treatment AEs of Special Interest				Y				
Reasons for Considering as a Serious Adverse Event				Y				

	Absolute				Change from Baseline			
	Summary		Individual		Summary		Individual	
	T	F	F	L	T	F	F	L
Pneumonia								
On-Treatment Pneumonias Incidence	Y ⁹			Y ³				
Details of on-treatment Pneumonia	Y ⁹			Y ³				
Post-Treatment Pneumonias Incidence	Y ⁹			Y ³				
Details of Post-treatment Pneumonia	Y ⁹			Y ³				
Bone Fractures								
On-Treatment Bone Fractures	Y			Y ³				
Post-Treatment Bone Fractures	Y			Y ³				
Radiography (Chest Imaging including X-Rays and CT Scan)								
On-Treatment Chest Imaging	Y			Y ³				
Post-Treatment Chest Imaging	Y			Y ³				
Liver Events								
Medical conditions for subjects with liver stopping events				Y				
Liver Event Results and Time of Event Relative to Treatment				Y				
Liver Event Substance Use				Y				
Liver Event Information for RUCAM Score				Y				
Liver Biopsy Details				Y				
Liver Imaging Details				Y				
On Treatment Laboratory Parameters								
Liver Function Tests		Y ⁶						
Chemistry Values for Subjects with at Least One Value Outside the Normal Range				Y				
Chemistry Data	Y	Y ⁴			Y	Y ⁵		
Chemistry Data Outside the Normal Range	Y							
Chemistry Changes from Baseline Relative to the Normal Range	Y							
Hematology Values for Subjects with at Least One Value Outside the				Y				

	Absolute				Change from Baseline			
	Summary		Individual		Summary		Individual	
	T	F	F	L	T	F	F	L
Normal Range								
Hematology Data	Y	Y ⁴			Y	Y ⁵		
Hematology Data Outside the Normal Range	Y							
Hematology Changes from Baseline Relative to the Normal Range	Y							
On Treatment Vital Signs								
Vital Sign Data (Pulse Rate, Sys BP, Dia BP)	Y			Y	Y			
12-Lead ECGs								
ECG Values	Y			Y ⁷	Y		Y ⁸	
ECG Findings	Y							
ECG Findings Shifts from Baseline	Y							
QTcF Categories	Y				Y			
ECG Abnormalities	Y			Y ⁷			Y ⁸	
ECG Abnormalities Occurring in at least 3% of Subjects in Either Treatment Group	Y							
Maximum Post-Baseline QTcF		Y ⁸				Y ⁸		

NOTES :

- T = Table, F = Figure, L = Listing, Y = Yes display generated.
 - Stats Analysis = Represents TFL related to any formal statistical analyses (i.e. modeling) conducted.
 - Summary = Represents TFL related to any summaries (i.e. descriptive statistics) of the observed raw data.
 - Individual = Represents FL related to any displays of individual subject observed raw data.
1. ASE Population
 2. ITT Population
 3. Combined listing for on-treatment and post-treatment.
 4. Separate box plots of change from baseline in maximum and minimum post-baseline values
 5. Separate scatter plots for maximum and minimum post-baseline versus baseline divided by ULN for maximum and LLN for minimum
 6. Trellis Display of Maximum Post-baseline Liver Function Test Values Versus Baseline Liver Function Test Values
 7. Listing of data only for subjects with any abnormal ECG finding.
 8. Empirical Distribution Function Plot
 9. Pneumonia are the cases recorded in Pneumonia Details CRF form
 10. Repeat for by country
 11. Trellis plot baseline vs post baseline

